6.0 MINIMIZATION OF BIAS

Potential sources of bias in this study may result from selection of subjects, treatment of subjects, and evaluation of study data. The following methods have been incorporated into the study to minimize potential bias.

- Subjects will be screened to confirm eligibility for enrollment with defined inclusion/exclusion criteria prior to enrollment
- Subject demographics will be collected at baseline on possible differences that may affect the primary objective
- All study clinicians, participating site personnel, and the Sponsor's personnel will be trained on their respective aspects of the study using standardized training materials
- All study clinicians will be trained on and required to follow the CIP

7.0 INVESTIGATORS

7.1 INVESTIGATOR SELECTION AND RESPONSIBILITIES

In order for the Investigators to participate in the study, they must meet the following criteria:

- Curriculum vitae (CV) providing evidence of sufficient training and experience in the management of patients with chronic pain.
- Has implanted and managed at least 12 patients with SCS devices within the past 12 months.
- The Investigator's participation in other clinical studies will not present a conflict of interest and will not interfere with the clinical study enrollment, study management, or study confidentiality.
- Is willing to provide any conflicts of interest details.
- Is willing to comply with all federal laws and regulations as well as IRB rules regarding clinical studies.

8.0 STUDY POPULATION

Subjects that are candidates for SCS, agreed to undergo an SCS temporary trial and that meet study eligibility criteria will be asked to participate in the study and will be required to sign informed consent prior to any study-related procedures or data collection occurring. It is expected that up to 15 subjects may be enrolled to screen for eligibility, and up to 10 subjects will undergo an SCS trial with the Algovita® Trial System. Subjects may either be male or female and must meet all eligibility criteria noted below which are typical eligibility criteria for SCS system post-market studies.

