Multi-Center Evaluation of Clinical Outcomes of Pulse Widths <500 μ sec and >1000 μ sec During a Temporary Spinal Cord Stimulation Trial

Title: Multi-Center Evaluation of Clinical Outcomes of Pulse Widths <500 μ sec and >1000 μ sec During a Temporary Spinal Cord Stimulation Trial

Protocol Number: TBD

Device: Nuvectra® Algovita® Spinal Cord Stimulation System

Sponsor: The Ohio Pain Clinic
[name]
[name]

Sponsor Contact: [name]
[name]
[name]
[contact]

Study Sites: TBD

Medical Monitor: [name]
Ohio Pain Clinic
[name]
[name]

Date of Protocol: TBD

Confidentiality Statement

The confidential information in this document is provided to you as an investigator or consultant for review by you, your staff, and the applicable Institutional Review Board. Your acceptance of this document constitutes agreement that you will not disclose the information contained herein to others without written authorization from .

Protocol Synopsis

Sponsor Contact Information Ohio Pain Clinic
[name]
[name]
[name]

Study Purpose The purpose of this study is to evaluate the effect of pulse widths <500 μ sec and >1000 μ sec on clinical outcomes during a temporary SCS trial.

Study Design and Scope The proposed study is a prospective, multi-center, two-arm, randomized, crossover design to be conducted at up to 10 sites. The study will enroll up to 100 subjects in order to include up to 10 subjects in the study per site. Subjects selected to participate in the trial have back and/or leg pain, have been evaluated as a candidate for SCS and have agreed to undergo a temporary SCS trial using the Algovita® system with percutaneous leads. Each subject will be followed during the trial period of approximately 7+-2 days. The study will end when the last subject has completed the trial period and exited. The expected enrollment period for this study is approximately six months. After exit from the clinical study, subjects will continue to be followed by their physician per usual care. All device and procedure-related AEs will be collected and reported per the study protocol.

Primary Effectiveness Objective Compare the change in the patient defined pain coverage map from baseline to the end of the 7+-2 day trial.

Secondary Effectiveness Objectives Secondary measures of therapy effectiveness will include:

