4.0 STUDY DESIGN

The proposed study is a prospective, single-center, two arm, randomized, crossover design to be conducted at The Ohio Pain Clinic. The study will enroll up to 100 subjects in order to assure at least 50 subjects in the study. Subjects selected to participate in the trial have back and/or leg pain, have been identified as a candidate for SCS and have agreed to undergo a temporary SCS trial using the Algovita® system with percutaneous leads. Each subject will be followed during the trial period of approximately 7 days.

The study will end when the last subject has completed the trial period or is exited. The expected enrollment period for this study is approximately three months. After exit from the clinical study, subjects will continue to be followed by their physician per usual care. All device and procedure-related AEs will be collected and reported per the study protocol.

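### Section 8.0 allows at most 10 treated subjects where section 4.0 needs at least 50, and the protocol is both multi-center over six months and single-center over three

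*Combined protocol and SAP*

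**What the plan says.** On the number of subjects, section 8.0 (Study Population) expects that "up to 15 subjects may be enrolled to screen for eligibility, and up to 10 subjects will undergo an SCS trial" with the study system. It gives no per-site qualifier. Section 4.0 (Study Design) says: "The study will enroll up to 100 subjects in order to assure at least 50 subjects in the study". The synopsis, under Study Design and Scope, says: "The study will enroll up to 100 subjects in order to include up to 10 subjects in the study per site". Section 8.3 (Sample Size) is a single sentence that limits the sample to 100.

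On centers and timing, the title begins "Multi-Center Evaluation of Clinical Outcomes of Pulse Widths" and the synopsis describes a "prospective, multi-center, two-arm, randomized, crossover design to be conducted at up to 10 sites", with an enrolment period of about six months. Section 4.0 describes a "prospective, single-center, two arm, randomized, crossover design to be conducted at The Ohio Pain Clinic" and adds: "The expected enrollment period for this study is approximately three months". The synopsis is itself mixed. Its Study Procedures text sends the patient to that same clinic for data collection and reprogramming, and has that clinic provide care after exit. The title page has "Study Sites: TBD".

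Section 9.1.2 treats anyone who signs consent as enrolled. Section 13.5 (Final Report) speaks of a pilot at one center, but the same sentence names a wireless stimulator and a different condition, so it appears to have been carried over from another study.

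**The concern.** Two basic features of the plan are stated in incompatible ways: how many subjects will be treated, and at how many centers over what period. The protocol gives no effect size, variability, power or dropout assumption, so these counts are all the sample-size information there is. A site or ethics committee that follows 8.0 would expect no more than 10 treated subjects. One that follows 4.0 would expect at least 50 at one clinic, and one that follows the synopsis would expect up to 100 across up to 10 sites. The number of centers also bears on how randomization is organized and on whether differences between sites need attention in the analysis.

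**Working it through.** The statements side by side:

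| Place | Centers | Enrolled | In the study or treated | Enrolment period |
|---|---|---|---|---|
| Title | multi-center | not given | not given | not given |
| Synopsis, Study Design and Scope | up to 10 | up to 100 | up to 10 per site | about 6 months |
| Synopsis, Study Procedures | visits and later care at one clinic | not given | not given | not given |
| 4.0 | one | up to 100 | at least 50 | about 3 months |
| 8.0 | not given | up to 15 | up to 10 treated | not given |
| 8.3 | not given | limit of 100, group not named | not given | not given |

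**Step 1: the protocol's own figure.** In the synopsis, 10 sites × 10 subjects per site = 100, which reproduces its ceiling. The synopsis counts are consistent with each other.

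**Step 2: 8.0 as worded against 4.0.** Minimum in 4.0 = 50. Maximum treated in 8.0 = 10. Shortfall = 50 − 10 = 40 treated subjects. A maximum of 10 cannot meet a minimum of 50. Nor do 15 enrolled and 10 treated match the figure of 100 in the synopsis, 4.0 and 8.3.

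**Step 3: 8.0 read as per-site limits (an assumption; the text does not say so).**
- Against the synopsis: up to 10 treated per site matches its limit of up to 10 subjects per site. The 15 and 10 are maxima, so they can operate under an overall cap of 100. For example, ten sites that each consent 10 and treat 5 to 10 give 10 × 10 = 100 consented and 50 to 100 treated. That stays within the per-site limits and the cap.
- Against 4.0: with one center, the per-site total is the whole-study total, 1 × 10 = 10. The shortfall is still 40.

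The per-site reading therefore reconciles 8.0 with the synopsis but not with 4.0.

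**Step 4: centers and enrolment period.** Up to 10 sites and one clinic cannot both be the design, and about six months and about three months cannot both be the enrolment period. This conflict does not depend on how 8.0 is read, nor on 13.5.

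**The case against.** The strongest reply is that 8.0 lost the words *per site*, that the site list is still open and the document is marked as a draft, and that three places agree on 100. Much of this stands. The shared figure of 10 makes the per-site reading plausible, and under it 8.0 and the synopsis agree. It does not help 4.0, which is single-center. An open site list explains why the count is unsettled, but not why firm statements about it disagree.

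A reader might infer more than the documents support:

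- *Per-site limits would break the cap.* Ten sites at 15 consented each would give 150, which is 50 over 100. That follows only if every site fills its maximum. The numbers are upper limits, so seven to ten sites can run within the cap.
- *The shortfall could also be put at 35 (50 − 15).* That sets subjects consented for screening against subjects in the study. Section 4.0 separates the two groups, so 40 is the like-for-like figure.
- *The sections imply conflicting ratios of enrolled to treated subjects.* Such ratios divide a ceiling by a floor or by another ceiling. Section 4.0 allows anything from 50 to 100 in the study out of 100 enrolled, and 10 out of 15 in 8.0 (about 67 per 100) lies within that range.
- *The loss of precision at 10 subjects can be quantified.* The documents give no standard deviation and do not specify the efficacy analysis, so any interval width would rest on assumptions from outside them.
- *Section 13.5 confirms a single-center study.* Its sentence concerns another device and condition, so it is supporting evidence at most.

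**Conclusion.** The contradiction stands and must be resolved. Section 8.0 as worded allows at most 10 treated subjects against a minimum of 50 in 4.0, a shortfall of 40. This takes the 50 to count treated subjects, which the protocol should confirm. Supplying *per site* in 8.0 would align it with the synopsis and leave the conflict with 4.0 in place. Independently, the protocol is multi-center in the title and synopsis (up to 10 sites, about six months in the synopsis) and single-center in 4.0 (about three months), with synopsis procedures written for one clinic. The documents do not show which design is intended. The finding is an inconsistency between sections; no calculation in the protocol is wrong, and it does not show that 50 or 100 subjects would be too few.

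**What to change.** - State one design, single-center or multi-center with the site count, and one enrolment period, in the title, the synopsis (including its procedures) and 4.0.
- State one cap on enrolled (consented) subjects and one target for treated subjects, identically in the synopsis, 4.0, 8.0 and 8.3. Say that the 50 counts treated subjects, if that is what is meant.
- Correct the 15 and 10 in 8.0, or label them as per site and subject to the overall cap. The label works only if the design is multi-center.
- Replace the sentence in 13.5 that refers to another device and condition; changing its site count alone would not be enough.

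The cost is protocol wording in the places listed. No increase in enrolment is asked for, and no visits or procedures are added.

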8.1 Inclusion Criteria

To be eligible for this study, patients **MUST**:

1. be eligible for SCS therapy according to the Algovita® SCS system Indications for Use statement
2. be undergoing a SCS trial using Algovita® SCS system
3. sign a valid, Institutional Review Board (IRB)-approved informed consent form.
4. be 18 years of age or older when written informed consent is obtained

8.2 Exclusion Criteria

To be eligible for enrollment in this study, the patients must **NOT**:

1. be contraindicated for an Algovita® SCS system
2. have a cognitive impairment or exhibits any characteristic, that would limit the study candidate's ability to assess pain relief or complete study assessments
3. have a life expectancy of less than 2 years
4. be participating in another clinical study that would confound data analysis
5. have a coexisting pain condition that might confound pain ratings
6. have a significant psychiatric disorder

8.3 Sample Size

The study sample size is limited to 100 subjects.

9.0 Methods and Procedure

9.1 DATA COLLECTION REQUIREMENTS

Subject data will be collected and documented on case report forms (CRFs). Drafts of the CRFs for this study are located in Appendix 17.

9.1.1 Subject Screening Procedure

Subjects will be screened from candidates for SCS, that have agreed to undergo an SCS temporary trial and that meet study eligibility. Subjects who meet these criteria will be asked to participate in the study and if they agree will be required to sign an informed consent prior to any study-related procedures or data collection occurring.

Assessments and Data Collection	Enrollment	Baseline	After Implant	Follow-up Visits	Study Exit
• Eligibility	✓				
• Medical history	✓				
• Physical exam					
• Informed consent	✓				
• Record demographics		✓			
• Brief Pain Inventory		✓			
• Record pain map		✓		✓	✓
• Implant and system information			✓		
• Record pain rating for current arm				✓	✓
• Record paresthesia and pain map for current arm					
• Document any AEs			✓		
• Record subject program preference					✓
• Record subject satisfaction and pain relief from each program					✓
• Document study exit reason & any					✓

Table 6-1: Summary of assessments at each visit

9.1.2 Informed Consent

Informed consent is defined as legally effective, documented confirmation of a subject's (or their legally authorized representative or guardian) voluntary agreement to participate in a particular clinical

investigation after information has been given to the subject on all aspects of the clinical investigation that are relevant to the subject's decision to participate. When a subject signs and dates the informed consent form, he/she is considered a subject enrolled in the study.

Prior to initiation of any study-specific procedures, subjects (or their legally authorized representative or guardian) must sign and date the informed consent form and Health Insurance Portability and Accountability Act (HIPAA) authorization, or equivalent, where required by law and IRB. Documentation that consent was obtained prior to any study-related procedures must be maintained in the subject's case history.

9.1.3 BASELINE VISIT

Confirm subject's eligibility for study participation and perform a Baseline visit. The following data will be collected by the study physician during this assessment and documented as appropriate:

- Relevant medical history (including diagnosis, prior treatment for chronic pain, past surgical procedures)
- Demographics
- Physical examination
- Collection of Brief Pain Inventory, pain-related ratings (NRS) and pain map

9.1.4 IMPLANT

The implant trial procedure will be performed within 28 calendar days following the Baseline Visit. Appropriately trained field staff will assist as necessary with the Algovita® Trial Lead implant. The recommended placement for the device will be determined by the physician and documented on the CRF. Information regarding the devices used, location, and procedure data will be collected on an Implant CRF. A Nuvectra® representative may be present during the implant procedure and may assist in the programming of the Algovita® system at the Investigator's direction.

9.1.5 FOLLOW-UP VISITS

Follow-up visits will occur at day 4 and 7 (+/-2) post-implantation. Data collected at these visits will be recorded on case forms (CRFs) and will include:

- Record paresthesia and pain map for current arm
- Record pain rating for current arm
- Document AEs
- Program subject with next arm parameters and document

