- Compare the change from baseline of pain scores between the two study arms. Pain scores are obtained using the Numeric Rating Score (NRS) administered at baseline and after completion of each arm of the study.
- Paresthesia distribution: At end of each arm, subjects will be asked to complete a diagram that shows distribution of paresthesia.
- At the end of the trial period, subjects will be asked to select their favorite program.
- At the end of the trial period, subjects will be asked to rate the quality of the pain relief achieved during the trial (from either arm) using the following scale; *Excellent, Very Good, Good, Fair or Poor*.
- At the end of the trial period, subjects will be asked to rate their overall satisfaction with the pain relief achieved during the trial (from either arm) using the following scale: *Very Satisfied, Satisfied, Neither Satisfied nor Unsatisfied, Unsatisfied, or Very Unsatisfied*.

Secondary Safety Objectives Secondary measures of therapy safety will include:

- Rate of device-related and/or procedure-related AEs from the Trial procedure through study completion.

Study Procedures After the subject has consented to the study, he or she will be enrolled in the clinical study and undergo a baseline evaluation. The patient will then be randomly assigned to arm one (pulse width <500 μ sec) or arm two (pulse width >1000 μ sec) and undergo an Algovita® trial procedures. Following the trial procedure, the subject's EPG will be set to the appropriate pulse width, based on the arm assigned, and then programmed to achieve optimal pain relief. For the next three days, the subject will evaluate pain relief generated by the 1st assigned program (arms).

After 3 days, the patient will visit the Ohio Pain Clinic for data collection and then reprogramming of the EPG for the next arm. For the next three days, the subject will evaluate the SCS therapy generated by the 2nd assigned program and then return to the clinic for data collection, removal of the leads and exit from the study. After the subject is exited from the study, he or she will be followed by the Ohio Pain Clinic per usual care. The data collection requirements are listed below.

Enrollment:

- Informed consent signed
- Confirmation of study eligibility

Baseline evaluation:

- Record pain ratings and pain map
- Relevant medical history
- Physical examination
- Brief Pain Inventory
- Demographics

After the lead implantation:

- Implant procedure

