- Document SCS products & lead configuration, electrode position and programmed parameters

4 and 7 day (+/- 2) Post-Implantation:

- Record pain map data
- Record pain rating for current arm
- Record paresthesia and pain map for current arm
- Document AEs
- Program subject with next arm parameters and document

[figure not shown]
Study Exit

- Record pain map data
- Record pain rating for current arm
- Record paresthesia and pain map for current arm
- Record program preference
- Record satisfaction and pain relief from each program
- Document study exit reason & AEs

TIME AND EVENTS SCHEDULE

Assessments and Data Collection	Enrollment	Baseline	After Implant	Follow-up Visits	Study Exit
• Eligibility confirmation	✓				
• Medical history	✓				
• Physical exam					
• Informed consent	✓				
• Record demographics		✓			
• Brief Pain Inventory		✓			
• Record pain map		✓			
• Implant and system information			✓		
• Record paresthesia and pain map for current arm	✓		✓	✓	✓
• Record pain rating for current arm	✓	✓	✓	✓	✓
• Document any AEs		✓	✓	✓	✓
• Record subject program preference					✓
• Record subject satisfaction and pain relief from each program					✓
• Document study exit reason & any AEs					✓

FLOWCHART

PROTOCOL HISTORY OF CHANGE
TBD

Original issue

Table of Contents

Page	
Protocol Title.....	i
Protocol Synopsis.....	ii
Protocol History of Change/ Summary of Bibliography Studies	vi
List of Abbreviations and Definitions	x
1.0 INTRODUCTION	8
2.0 OBJECTIVES	10
2.1 Primary Objective.....	10
2.2 Secondary Objectives	10
3.0 REGULATORY CLASSIFICATION	11
4.0 DEVICE.....	11
4.1 ALGOVITA® SPINAL CORD STIMULATION SYSTEM.....	11
5.0 STUDY DESIGN.....	12
5.1 OVERVIEW OF DATA COLLECTION AT STUDY VISITS	12
6.0 ENDPOINTS	13
6.1 PRIMARY EFFECTIVENESS ENDPOINT.....	13
6.2 SECONDARY ENDPOINTS.....	13
7.0 MINIMIZATION OF BIAS.....	14
8.0 INVESTIGATORS	15
8.1 INVESTIGATOR SELECTION AND RESPONSIBILITIES	15
9.0 STUDY POPULATION	16
9.1 Inclusion Criteria.....	16
9.2 Exclusion Criteria	16
9.3 Sample Size	16
10.0 Methods and Procedure.....	17
10.1 DATA COLLECTION REQUIREMENTS.....	17
10.1.1 Subject Screening Procedure.....	17
10.1.2 Informed Consent	17
10.1.3 BASELINE VISIT	18
10.1.4 IMPLANT	18
10.1.5 FOLLOW-UP VISITS.....	18
10.1.6 STUDY EXIT.....	18
11.0 ADVERSE EVENT REPORTING.....	20
11.1 ADVERSE EVENTS.....	20
11.2 ANTICIPATED ADVERSE DEVICE EFFECTS	20
11.3 UNANTICIPATED ADVERSE DEVICE EFFECTS.....	21
12.0 STATISTICS	22
12.1 Study Population.....	22
12.2 Safety Analysis	22

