9.1.6 STUDY EXIT

A Study Exit CRF must be completed for any subject who signed an informed consent form, as they are considered enrolled in the study. Data to be collected at this visit includes:

- Record paresthesia and pain map for current arm
- Record pain rating for current arm
- Record program preference

- Record satisfaction and pain relief from each program
- Study exit date and reason for study exit

Additional data that will be collected as they occur include:

- Device or procedure related AEs
- Technical Observations/Device Deficiencies
- Surgical Interventions

The following scenarios may lead to study exit and will require completion of a Study Exit CRF.

- Inclusion/exclusion criteria not met
- Subject ineligibility for implant, in the opinion of the study physician
- SCS lead removal without re-implantation
- Implant attempted, however no SCS was implanted
- Voluntary withdrawal by subject
- Investigator chooses to withdraw a subject
- Failure to maintain adequate study compliance
- Subject Death

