11.0 STATISTICS

11.1 Study Population

All patients who received treatment will be included in an intent-to-treat (ITT) analysis. A per protocol analysis will also be conducted if there are protocol violators.

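### The visit windows in section 9.1.5 do not protect the intended three days on each program; on two of three readings, in-window visits can leave one day on the second

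*Combined protocol and SAP*

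**What the plan says.** The Study Procedures part of the synopsis describes two equal periods. The subject evaluates the first program for three days. Then "After 3 days, the patient will visit the Ohio Pain Clinic for data collection and then reprogramming of the EPG for the next arm". The second period has the same length: "For the next three days, the subject will evaluate the SCS therapy generated by the 2nd assigned program", followed by return to the clinic for data collection, lead removal and exit. Neither three-day period is given a tolerance.

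The visit schedule is written differently. Section 9.1.5 states "Follow-up visits will occur at day 4 and 7 (+/-2) post-implantation", and the synopsis repeats it as "4 and 7 day (+/- 2) Post-Implantation". Both visits are anchored to implantation, and reprogramming to the next arm is listed among the tasks at these visits. The synopsis also gives an overall length: "Each subject will be followed during the trial period of approximately 7+-2 days".

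Section 9.1.6 has the exit form record "Study exit date and reason for study exit". Section 11.1 says "A per protocol analysis will also be conducted if there are protocol violators", without defining a violator.

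**The concern.** Each program is judged at the end of its own period, by pain map, paresthesia map and NRS, and the subject states a preference at exit. The comparison between pulse widths is meant to be made within the same subject, so it assumes roughly comparable time on each program. A subject with one day on one program and three or more on the other contributes a difference that mixes pulse width with length of exposure.

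Nothing in section 9.1.5 ties the exit visit to the switch, sets a minimum gap or points back to the three-day statement. A site that schedules from 9.1.5 alone can stay inside every window and still give very unequal periods. Such a subject is in window under 9.1.5 but at odds with the synopsis. Whether that subject belongs in the per-protocol set would then have to be decided after the data are in.

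**Working it through.** **Inputs.** Intended time per program: 3 days (synopsis, Study Procedures). Visits: day 4 and day 7, ±2, counted from implantation (9.1.5 and synopsis). Total length: 7 ±2 days (synopsis, Study Design and Scope). The day number of implantation is not stated, so both conventions are shown.

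**Notation.** The switch is on day s and exit on day e. Time on the second program is d = e − s. Time on the first is a = s − 1 if implantation is day 1, or a = s if it is day 0.

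**Nominal schedule.** With s = 4 and e = 7, d = 7 − 4 = 3, as intended. The first period is 4 − 1 = 3 days with implantation as day 1, or 4 days with day 0. Only day 1 reproduces the synopsis's 3 + 3.

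**Three readings of ±2.**

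- A: it applies to each visit separately, so s = 2 to 6 and e = 5 to 9.
- B: it applies to day 7 only, so s = 4 and e = 5 to 9.
- C: both visits slide together, so e = s + 3 with s = 2 to 6 and e = 5 to 9.

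| Reading | Second program | First program, implant = day 1 | First program, implant = day 0 |
|---|---|---|---|
| A | 1 to 7 days | 1 to 5 | 2 to 6 |
| B | 1 to 5 days | 3 | 4 |
| C | 3 days | 1 to 5 | 2 to 6 |

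The second-program column does not depend on the day count, because d = e − s. The 1-day minimum there arises at (s, e) = (4, 5), (5, 6) and (6, 7) on reading A, and at (4, 5) on reading B.

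**Enumeration for reading A.** There are 5 × 5 = 25 whole-day pairs. Three give d ≤ 0: (5, 5), (6, 6) and (6, 5). That leaves 25 − 3 = 22 feasible pairs. Of these, 3 have d = 1 and 4 have d = 2, so 7 give fewer than three days on the second program.

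| Among the 22 feasible pairs | Implant = day 1 | Implant = day 0 |
|---|---|---|
| 1 day on one program | 8 (5 with a = 1, plus 3 with d = 1) | 3 (all d = 1) |
| Periods differ by 3 days or more | 9 | 10 |
| Largest ratio | 7:1 at (2, 9) | 6:1 at (6, 7) |

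Pairs differing by 3 days or more, counted by switch day 2, 3, 4, 5, 6:

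- implant = day 1: 4 + 2 + 0 + 1 + 2 = 9;
- implant = day 0: 3 + 1 + 1 + 2 + 3 = 10.

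**Proposed rule, implant = day 1.** With s = 3, 4 or 5, a = 2 to 4. With e = s + 2, 3 or 4, d = 2 to 4. Exit runs from 3 + 2 = 5 to 5 + 4 = 9. The largest difference is 4 − 2 = 2 days and the largest ratio 2:1. All 3 × 3 = 9 pairs lie inside the present reading-A windows, so 22 − 9 = 13 currently allowed pairs would fall out.

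**The case against.** The synopsis is current protocol text and states the three-day duration for both programs. If those statements govern, ±2 is only a visit window, and a one-day period would conflict with the protocol even when the visit is in window. The nominal days agree with that intent. This has force: the plan does state an intended duration. What stands against it is that the statement carries no tolerance and 9.1.5 does not refer to it. The visit section therefore permits what the synopsis does not intend.

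A reader might infer that one day on a program is possible however the window is read. The documents do not support that. If the visits slide together and implantation is day 0, the shortest period is 2 days.

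A reader might also infer a biased comparison. The documents do not show one. With randomized order, timing unrelated to treatment or response mainly adds noise. Section 6.0 lists no masking among its measures against bias, so the text does not rule out a disappointing program being ended early, but nothing indicates that this happens. Nor do the documents say how quickly the effect of a program builds up.

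It is also fair to say that the counts describe allowed combinations, and that 7:1 needs the earliest switch and the latest exit in one subject. Programming records and the exit date may let time on program be derived, and the flowchart and case report forms, which are not visible, may add detail. A derivable duration is still not a rule for what is acceptable.

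**Conclusion.** The point holds as a gap between the intended exposure and the visit rule. With ±2 on both visits or on day 7 only, a schedule wholly within 9.1.5 can leave 1 day on the second program against 3 intended, whichever day implantation is called. If the visits slide together, only the first program is affected, and its minimum is 1 day or 2 depending on the unstated day count.

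The conclusion assumes whole-day scheduling and that 9.1.5 is applied as written. The consequence for the results cannot be quantified from the documents. The change is worth making as an inexpensive safeguard, and the point is not evidence that the comparison is invalid.

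**What to change.** In section 9.1.5, with matching wording in the synopsis:

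- define implantation as day 1;
- set the switch visit at day 4 ±1;
- time the exit visit from the switch, at 3 ±1 days later;
- record the date and time of each program change;
- in section 11.1, treat less than 2 days on either program as a deviation for the per-protocol set.

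The ±1 tolerance and the 2-day cut-off are practical choices; the documents give no time to effect from which to derive them. A sponsor with such data could choose others, provided exit stays anchored to the switch.

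The cost is protocol and case report form wording and tighter scheduling of two existing visits, with no extra subjects or visits. The main drawback is more recorded deviations: the 13 of 22 pairs counted above, which assume implantation as day 1 and ±2 on both visits.
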